### **8.3. Adverse Events**

All AEs will be coded using MedDRA.

The following are considered protocol-defined AEs of special interest: events of anaphylaxis and severe hypersensitivity reactions and ophthalmic events of at least moderate severity.

Summaries will be presented for all treatment-emergent AEs (overall and by severity), AEs determined by the investigator to be treatment-related AEs (defined as related or with missing relationship (overall and by severity), serious AEs, protocol-defined AEs of special interest, AEs causing withdrawal from treatment, and non-serious AEs. Additionally the injection site reactions recorded as AEs will be summarized separately.

The incidence of AEs will be summarized using descriptive statistics by SOC and PT (all treatment-emergent AEs overall will also be presented by just PT category). Patients are counted only once in each SOC category, and only once in each PT category. For the summaries by severity, patients are counted at the greatest severity. AEs with the missing flag indicating serious will be excluded from the summary of serious AEs but included in the summary of non-serious AEs.

Listings for deaths, AEs, serious AEs, AEs causing withdrawal from treatment, injection site-related AEs, and protocol defined AEs of special interest will be presented.

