The relationship of each adverse event to IMP and study procedures, and the severity and seriousness of each adverse event, as judged by the investigator, must be recorded as described in Section 7.1.3 and Section 7.1.4.

Further details are given in the Safety Monitoring Plan.

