7.1.5.1. Definition of a Serious Adverse Event

A serious adverse event is an adverse event occurring at any dose that results in any of the following outcomes or actions:

- results in death
- is life-threatening adverse event (ie, the patient was at risk of death at the time of the event); it does not refer to an event which hypothetically might have caused death if it were more severe
- requires inpatient hospitalization or prolongation of existing hospitalization, which means that hospital inpatient admission or prolongation of hospital stay were required for treatment of an adverse event, or that they occurred as a consequence of the event
- Hospitalizations scheduled before the patient signed the ICF will not be considered serious adverse events, unless there was worsening of the preexisting condition during the patient's participation in this study.
- results in persistent or significant disability/incapacity (refers to a substantial disruption of one's ability to conduct normal life functions)
- is a congenital anomaly/birth defect
- an important medical event that may not result in death, be life-threatening, or require hospitalization, but may jeopardize the patient and may require medical intervention to prevent one of the outcomes listed in this definition

Examples of such events are intensive treatment in an emergency room or at home for allergic bronchospasm; blood dyscrasias or convulsions that do not result in hospitalization; or the development of drug dependency or drug abuse. Note: Any suspected transmission of an infectious agent via a medicinal product is considered an important medical event.

All occurrences of possible drug-induced liver injury that meet Hy's law criteria, defined as all of the below, must be reported by the investigator to the sponsor as a serious adverse event:

- ALT or AST increase of $>3 \times$ ULN
- total bilirubin increase of $>2 \times$ ULN
- absence of initial findings of cholestasis (ie, no substantial increase of ALP)

An adverse event that does not meet any of the criteria for seriousness listed above will be regarded as a nonserious adverse event.

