7.1.5.3. Reporting a Serious Adverse Event

7.1.5.3.1. Investigator Responsibility

To satisfy regulatory requirements, all serious adverse events that occur during the study, regardless of judged relationship to administration of the IMP, must be reported to the sponsor by the investigator. The event must be reported within 24 hours of when the investigator learns about it. Completing the serious adverse event form and reporting the event must not be delayed, even if not all the information is available. The investigator does not need to actively monitor patients for adverse events once this study has ended.

Serious adverse events occurring to a patient after the last administration of IMP of that patient has ended should be reported to the sponsor if the investigator becomes aware of them.

The serious adverse event form should be sent to the local safety officer (LSO) or designee (a contract research organization [CRO] in a country without a sponsor LSO) (contact information is in the Clinical Study Personnel Contact Information section); the LSO will forward the report to the sponsor's GPSP department.

The following information should be provided to record the event accurately and completely:

- study number
- investigator and investigational center identification
- patient number
- onset date and detailed description of adverse event
- investigator's assessment of the relationship of the adverse event to the IMP (no reasonable possibility, reasonable possibility)

Additional information includes:

- age and sex of patient
- date of first dose of IMP
- date and amount of last administered dose of IMP

- action taken
- outcome, if known
- severity
- explanation of assessment of relatedness
- concomitant medication (including doses, routes of administration, and regimens) and treatment of the event
- pertinent laboratory or other diagnostic test data
- medical history
- results of dechallenge/rechallenge, if known
- for an adverse event resulting in death
 - cause of death (whether or not the death was related to IMP)
 - autopsy findings (if available)

Each report of a serious adverse event will be reviewed and evaluated by the investigator and the sponsor to assess the nature of the event and the relationship of the event to the IMP, study procedures, and to underlying disease.

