9.7. Safety Analysis

Safety analyses will be performed on the safety analysis set (Section 9.2.3).

Safety assessments and time points are provided in Table 4.

All adverse events will be coded using the Medical Dictionary for Regulatory Activities. Each patient will be counted only once in each preferred term or system organ class category for the analyses of safety. Summaries will be presented for all adverse events (overall and by severity), adverse events determined by the investigator to be related to test IMP (ie, reasonable possibility; see Section 7.1.4) (defined as related or with missing relationship) (overall and by severity), serious adverse events, and adverse events causing withdrawal from the study. Summaries will be presented by treatment group and for all patients. Patient listings of serious adverse events and adverse events leading to withdrawal will be presented.

Changes in laboratory, ECG, eC-SSRS, and vital signs measurements data will be summarized descriptively. All values will be compared with the predefined criteria to identify potentially clinically significant values or changes, and such values will be listed.

The use of concomitant medications will be summarized by therapeutic class using descriptive statistics. Concomitant medications will include ECT and all medications taken while the patient

is treated with IMP. Patients who begin prohibited therapies during the study will be discontinued from the study (eg, ECT, vagus nerve stimulation, direct current therapy, transcutaneous supraorbital stimulation, and other forms of electrical stimulation). Complete discontinuation criteria are provided in Section 4.3.

Safety data will be summarized descriptively overall, by treatment group, and by study phase. For continuous variables, descriptive statistics (n, mean, standard deviation, median, minimum, and maximum) will be provided for actual values and changes from randomization visit (day 1) to each time point. For categorical variables, patient counts and percentages will be provided. Descriptive summaries of serious adverse events and patient withdrawals due to adverse events will be provided as well.

If any patient dies during the study, a listing of deaths will be provided and all relevant information will be discussed in the patient narrative included in the CSR.

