If data are processed from other sources (eg, central laboratory, bioanalytical laboratory, central image center, electronic diary data, electronic patient-reported outcome tablet), these data will be sent to the investigational center, where they will be retained but not transcribed to the eCRF, unless otherwise noted in the protocol. These data may also be sent electronically to the sponsor (or organization performing data management). All patient data must have supportive original source documentation in the medical records, or equivalent, before they are transcribed to the eCRF. Data may not be recorded directly on the eCRF and considered as source data unless the sponsor provides written instructions specifying which data are permitted to be recorded directly to the eCRF.

For patients who enter a study but do not meet the entry criteria, at a minimum, data for screening failure reason, demography, and adverse events from the time of informed consent will be entered in the eCRF.

Data Quality Control

Data Management is responsible for the accuracy, quality, completeness, and internal consistency of the data from this study. Oversight will be carried out as described in the sponsor's SOPs for clinical studies. Day-to-day data management tasks for this study are delegated to a contract organization, and these functions may be carried out as described in the SOPs for clinical studies at that organization. These SOPs will be reviewed by the sponsor before the start of data management activities.

Data will be verified by the study monitor using the data source and reviewed by Data Management using both automated logical checks and manual review. Data identified as erroneous, or data that are missing, will be referred to the investigational center for resolution through data queries. Any necessary changes will be made in the clinical database, and data review and validation procedures will be repeated as needed. Data from external sources will be compared with the information available in the CDMS, and any discrepancies will be queried.

Applicable terms will be coded according to the coding conventions for this study.

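### SAP 8.3 counts adverse events with a blank seriousness flag as non-serious, although the same section counts a blank relationship as related

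*SAP*

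**What the plan says.** SAP 8.3 (Adverse Events) sets two rules for incomplete AE records. For causality, the related-event summary covers "treatment-related AEs (defined as related or with missing relationship", so a blank relationship counts as related. For seriousness, "AEs with the missing flag indicating serious will be excluded from the summary of serious AEs but included in the summary of non-serious AEs", so a blank flag counts as not serious.

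Protocol 9.7 (Safety Analysis) contains the first rule, describing related events as "defined as related or with missing relationship) (overall and by severity". It has no rule for missing seriousness.

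Two other parts of the protocol bear on what a blank flag means:

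- Section 7.1.2 requires that "the severity and seriousness of each adverse event, as judged by the investigator, must be recorded".
- Section 7.1.5.1 says that "An adverse event that does not meet any of the criteria for seriousness listed above will be regarded as a nonserious adverse event".

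Neither document plans a sensitivity summary for events with missing seriousness.

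**The concern.** A blank seriousness flag means that no assessment was recorded. The SAP tabulates it as though the investigator had judged the event not serious. The section's other missing-data rule goes the opposite way and assigns the blank to the less favourable category. The SAP does not explain why the two differ.

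Other SAP conventions also take the less favourable value. Severity is counted at the patient's highest grade (8.3), the overall ECG interpretation uses the worst finding after baseline (8.8), and patients who leave early are counted as not achieving the 50% reduction (6.3.2.1). The seriousness rule stands apart from these.

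What is at stake is the serious-AE table. An event that was in fact serious but has a blank flag at lock would be missing from that table and would appear in the non-serious one. AE occurrence is a stated safety endpoint, and serious AEs are one of the summaries that protocol 9.7 requires.

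**Working it through.** The plan gives no figure to reproduce here. The check compares the rules and then works out direction and scale.

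**1. The two rules in SAP 8.3**

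| Item left blank | Counted as | Direction |
|---|---|---|
| Relationship to study drug | Related | Less favourable |
| Seriousness | Not serious | More favourable |

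**2. Does the protocol imply that blank means not serious?** No. Section 7.1.5.1 makes an event nonserious when it meets none of the listed criteria, which is the result of an assessment. Section 7.1.2 makes that assessment mandatory for every AE. A blank is therefore missing data, not an implied negative. Equally, the SAP rule contradicts nothing in the protocol, because protocol 9.7 is silent on the matter.

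**3. Direction of the error.** For each event whose flag is still blank at lock:

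| True status | Error in serious count, SAP rule | Error in serious count, opposite rule |
|---|---|---|
| Serious | -1 | 0 |
| Not serious | 0 | +1 |

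Under the SAP rule the error is 0 or -1 and never positive. The rule makes no reference to treatment, so this is the same in both arms.

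**4. How often would it apply?** Rarely, on the documents' own safeguards:

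- Seriousness must be recorded for every AE (protocol 7.1.2).
- "Data identified as erroneous, or data that are missing, will be referred to the investigational center for resolution through data queries" (protocol Appendix L).
- Serious events also reach the sponsor on a separate form: "The event must be reported within 24 hours of when the investigator learns about it" (protocol 7.1.5.3.1).
- SAP 8.3 lists all AEs, so the event remains findable. The rule covers summaries only, and the SAP does not say whether a blank-flag event enters the serious-AE listing.

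**5. Scale.** Inputs: about 170 patients per group (SAP 2.4). The number of patients affected is an assumption, since the documents give none. Patients are counted once per category, so a group's overall serious-AE incidence falls only when the blank-flag event is the patient's sole serious event.

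- Change in incidence = k / 170, where k is the number of such patients in the group.
- k = 1: 1/170 = 0.0059, or about 0.6 percentage points.
- k = 3: 3/170 = 0.0176, or about 1.8 percentage points.
- k = 0: no change.

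The range for k from 1 to 3 is illustrative. Given step 4, zero is entirely plausible.

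**The case against.** The strongest reply is that this is a reporting preference with almost nothing to act on. To do harm, an event must be serious, have a blank flag, survive the data queries and go uncorrected from its own serious-AE form. Even then it stays in the overall AE summary and listing, and deaths, withdrawals due to AEs and events of special interest are presented separately. Relatedness and seriousness also differ in kind. Causality is a judgement, whereas seriousness rests on outcome criteria and has its own expedited channel, so the absence of a serious-AE report is informative. In the earlier Phase 3 trials summarised in protocol 1.2.2.2, serious AEs were infrequent and injection-site reactions were the most frequent treatment-related events. A random blank is therefore more likely to be non-serious, and counting it as serious could put a trivial event into the serious-AE table.

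Much of this stands. The effect is small, the protocol is not contradicted, and the opposite rule has an error of its own. It does not justify the rule as written. A missing-data convention matters only for records that escape the queries, and for those the SAP takes the favourable value without saying why. The argument from the absence of a serious-AE form would support a rule that depends on checking for one, and the SAP rule has no such condition.

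Three stronger readings are tempting, and the documents support none of them:

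- **That the rule favours fremanezumab over placebo.** It applies identically to both groups, and in the double-blind phase the investigators who judge seriousness are blinded. It can understate absolute counts; nothing shows that it tilts the comparison.
- **That the absence of a data monitoring committee makes it worse.** SAP 2.5.2 places all planned analyses after final database lock, so a table rule cannot affect oversight during the trial. Protocol 3.4 bases ongoing review on serious events as sites report them.
- **That one misfiled event would remove a sizeable share of the serious events.** The documents give no expected serious-AE rate for this trial, and SAP 8.1 summarises the double-blind phase by group and each period separately. A percentage of a pooled, assumed count has no basis in them.

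**Conclusion.** The point holds as a minor one. SAP 8.3 resolves missing seriousness in the favourable direction and missing relationship in the unfavourable direction, without explanation. For flags still blank at lock, the serious-AE count can only stay the same or fall, in both arms alike.

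The expected size is small. Each affected patient costs a group about 0.6 percentage points of incidence, assuming about 170 patients in the group and that the blank-flag event is the patient's only serious one. Whether any such patient will exist is unknown, and the protocol's safeguards make it unlikely. Efficacy results, error control and safety oversight during the trial are unaffected.

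**What to change.** Replace the sentence on missing seriousness in SAP 8.3 with a rule in two parts:

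1. Before database lock, every AE with a blank seriousness flag is queried and reconciled against the serious-AE reports.
2. Any AE still blank after that is counted in the serious-AE summary, left out of the non-serious summary and flagged in the AE listing. A separate seriousness-missing row would be an acceptable alternative to counting it as serious, and would avoid imputing in either direction.

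The cost is one sentence and a small programming change. If no blanks remain, the tables do not change. If some do, serious AEs may be slightly overcounted; the flag in the listing lets a reader see which events are involved.

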#### 8.4. Deaths

If any patient dies during the study all relevant information will be discussed in the patient’s narratives included in the CSR.

#### 8.5. Clinical Laboratory Tests

Laboratory test results will be presented in standard international (SI) units.

Summary statistics for chemistry, hematology, urinalysis, and coagulation laboratory tests will be presented at baseline, weeks 4, 8, 12, and 24, and last on study assessment (double-blind and open-label). Laboratory values and changes from baseline to each visit and last on study assessment will be summarized using descriptive statistics. Listings of all individual patients’ laboratory tests will be presented.

Shifts (below, within, and above the normal range) from baseline to each visit and last on study assessment will be summarized using patient counts.

Summaries of potentially clinically significant abnormal values will include all postbaseline values (including scheduled, unscheduled, and early termination visits). The incidence of potentially clinically significant abnormal values will be summarized for laboratory variables using descriptive statistics with the criteria specified in [Table 3](#).

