- i. The patient has a history of clinically significant cardiovascular disease or vascular ischemia (such as myocardial, neurological [eg, cerebral ischemia], peripheral extremity ischemia, or other ischemic event) or thromboembolic events (arterial or venous thrombotic or embolic events), such as cerebrovascular accident (including transient ischemic attacks), deep vein thrombosis, or pulmonary embolism.
- j. The patient has a known infection or history of human immunodeficiency virus, tuberculosis, any history of Lyme disease, or chronic hepatitis B or C infection.
- k. The patient has a past or current history of cancer, except for appropriately treated non-melanoma skin carcinoma.
- l. The patient is a pregnant or nursing female or plans to become pregnant during the study, including the 6-month period after the administration of the last dose.
- m. [Revision 1] The patient has a history of hypersensitivity reactions to injected proteins, including monoclonal antibodies, or a history of Stevens-Johnson Syndrome or toxic epidermal necrolysis syndrome.
- n. The patient has participated in a clinical study of a new chemical entity or a prescription medicine within 2 months of the screening visit (V1), or 3 months in case of biologics if the half-life of the biologics is unknown or 5 half-lives, whichever is longer, or is currently participating in another study of an IMP (or a medical device).

- o. [Revision 1] The patient has failed treatment (based on tolerability and/or a lack of efficacy) with any monoclonal antibodies targeting the CGRP pathway (erenumab, eptinezumab, galcanezumab, or fremanezumab) or have taken the medications within 5 half-lives of the screening visit (V1) or take them during the study.
- p. The patient has any finding in the baseline 12-lead ECG considered clinically significant in the judgment of the investigator.
- q. The patient has any finding that, in the judgment of the investigator, is a clinically significant abnormality, including serum chemistry, hematology, coagulation, and urinalysis test values (abnormal tests may be repeated for confirmation).
- r. The patient has hepatic enzymes (ALT, AST, and ALP) $>1.5 \times$ the upper limit of the normal range after confirmation in a repeat test or suspected hepatocellular damage that fulfills the criteria for Hy's law at the screening visit (V1).

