### 4.2. Specification of Baseline Values

For migraine days, the baseline value is the total number of migraine days during the 28-day baseline period. If the baseline period is greater or less than 28 days, the baseline value will be normalized to 28 days. In addition, if the baseline period is 28 days but there are days with missing diary, the baseline value will be normalized to 28 days.

For all other assessments, the baseline value is the last observed data prior to the first dose of study drug.

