**Table 3: Criteria for Potentially Clinically Significant Laboratory Values**

Test	Criterion value
Serum chemistry	
ALT	≥3x ULN
AST	≥3x ULN
ALP	≥3x ULN
GGT	≥3x ULN
LDH	≥3x ULN
BUN	≥10.71 mmol/L
Creatinine	≥177 μmol/L
Uric acid	Men
	Women
	≥625 μmol/L
	≥506 μmol/L
Bilirubin (total)	≥34.2 μmol/L
Hematology	
Hematocrit	Men
	Women
	<0.37 L/L
	<0.32 L/L
Hemoglobin	Men
	≤115 g/L

Test	Criterion value
Women	≤95 g/L
WBC counts	≤3 x 10  /L ≥20 x 10  /L
Eosinophils	≥10%
ANC	≤1 x 10  /L
Platelet counts	≤75 x 10  /L ≥700 x 10  /L
Urinalysis	
HGB	≥2 unit increase from baseline
Glucose	≥2 unit increase from baseline
Ketones	≥2 unit increase from baseline
Total protein	≥2 unit increase from baseline
Coagulation	
INR	>1.5

ALP=alkaline phosphatase; ALT=alanine aminotransferase; ANC=absolute neutrophil count AST=aspartate aminotransferase; BUN=blood urea nitrogen; GGT=gamma-glutamyl transpeptidase; HGB=hemoglobin; INR=international normalized ratio; LDH=lactate dehydrogenase; ULN=upper limit of normal range; WBC=white blood cell.

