### 8.7. Vital Signs

Summary statistics for vital signs (pulse, systolic and diastolic blood pressure, body temperature, and respiratory rate) will be presented at baseline, weeks 4, 8, 12, and 24, and last on study assessment (double-blind and open-label). Vital signs values and changes from baseline to each visit and last on study assessment will be summarized using descriptive statistics.

Summaries of potentially clinically significant abnormal values will include all postbaseline values (including scheduled, unscheduled, and early termination visits). The incidence of potentially clinically significant abnormal values will be summarized using descriptive statistics with the criteria specified in [Table 4](#).

[Table 4](#) specifies the criteria for identifying vital signs as potentially clinically significant abnormal values. Note that in order to qualify as potentially clinically significant abnormal, a value needs to meet both criteria below: ie, have a value beyond the criterion value and a change of at least the magnitude specified in the change relative to baseline column.

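### The summary of potentially clinically significant laboratory values does not separate abnormalities already present before the first dose from new ones

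*SAP*

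**What the plan says.** SAP 8.5 plans a summary of potentially clinically significant laboratory values by period and treatment group. Its scope is set by this sentence: "Summaries of potentially clinically significant abnormal values will include all postbaseline values (including scheduled, unscheduled, and early termination visits"). The statistic follows: "The incidence of potentially clinically significant abnormal values will be summarized for laboratory variables using descriptive statistics with the criteria specified in" Table 3. No numerator or denominator rule is given.

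Table 3 uses absolute limits for serum chemistry, hematology and INR (for example eosinophils at or above 10%, total bilirubin at or above 34.2 μmol/L, GGT at or above 3 times the upper limit of normal). Only the urinalysis rows refer to the patient's own starting value: "≥2 unit increase from baseline". For vital signs, SAP 8.7 requires that a patient "have a value beyond the criterion value and a change of at least the magnitude specified in the change relative to baseline column".

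SAP 4.2 defines one baseline for laboratory data: "For all other assessments, the baseline value is the last observed data prior to the first dose of study drug". No separate baseline is defined for the open-label period. The other planned laboratory outputs are descriptive statistics with change from baseline, individual listings, and shift tables: "Shifts (below, within, and above the normal range) from baseline to each visit and last on study assessment will be summarized using patient counts".

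**The concern.** A table of this kind is usually read as showing what appeared after dosing. Under the rule as written, a patient whose eosinophils, bilirubin or uric acid was beyond the limit on day 1 and stays there enters the count on the same footing as a patient who crossed the limit on treatment.

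What is at stake is the reading of the absolute safety rates. In the double-blind period the placebo column shows the same background, so the comparison keeps its direction. In the open-label period every patient receives 675 mg and there is no concurrent control. A persisting abnormality, whether from before the first dose or from the double-blind period (placebo included), then appears in a post-675 mg rate with nothing to mark it.

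**Working it through.** **Plan's own figure.** The documents give no expected rate of such values, so there is nothing to reproduce. The check is a reading of the text, followed by an illustration.

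**Step 1: do other rules remove baseline cases?**
- Numeric entry limits (Protocol 4.2, criteria r and s) cover ALT, AST and ALP (above 1.5 times the upper limit of normal) and creatinine (same multiple). The Table 3 limit for the three enzymes is 3 times, so a pre-existing case is unlikely. For creatinine, Table 3 uses 177 μmol/L. The entry limit lies below that if the upper limit of normal is under 177/1.5 = 118 μmol/L, a figure the documents do not give.
- For GGT, LDH, BUN, uric acid, bilirubin, hematocrit, hemoglobin, white cells, eosinophils, neutrophils, platelets and INR, entry rests mainly on investigator judgment (criterion q). Protocol 7.4 lets an out-of-range result be classed as not clinically significant, so such a patient can enter.

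**Step 2: does another planned summary give the split?**
- Shift tables use below, within and above normal. A value slightly above normal and one beyond the Table 3 limit fall in the same cell.
- Listings show each value but give no count. Protocol 9.7 adds only a listing.
- Baseline values exist: Protocol Table 4 schedules safety laboratory tests at visits 1 to 6.

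**Step 3: illustration.** Let p0 be the share beyond the limit at baseline, r the share of those beyond it again after baseline, and q the new-onset rate in the rest. All three are assumptions. The documents supply only n, about 170 per arm (SAP 2.4).

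Reported rate = p0·r + (1 − p0)·q. Pre-existing share = p0·r / reported rate.

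Example with p0 = 3%, r = 1, q = 1%: pre-existing 170 × 0.03 = 5.1 patients; new 170 × 0.97 × 0.01 = 1.6; total 6.7, or 3.97%, of which 76% is pre-existing.

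| q | p0 | Reported rate, r = 0.5 (pre-existing share) | Reported rate, r = 1 (pre-existing share) |
|---|---|---|---|
| 1% | 0 | 1.00% (0%) | 1.00% (0%) |
| 1% | 1% | 1.49% (34%) | 1.99% (50%) |
| 1% | 3% | 2.47% (61%) | 3.97% (76%) |
| 1% | 5% | 3.45% (72%) | 5.95% (84%) |
| 2% | 1% | 2.48% (20%) | 2.98% (34%) |
| 2% | 3% | 3.44% (44%) | 4.94% (61%) |
| 2% | 5% | 4.40% (57%) | 6.90% (72%) |

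**Step 4: effect on the arm comparison.** With the same p0 and r in both arms, the reported difference is (1 − p0)(q1 − q2), which keeps its sign. Take true new-onset rates of 2% and 1%, with r = 1. At p0 = 1% the reported rates are 2.98% and 1.99%, a difference of 0.99 points and a ratio of 1.50. At p0 = 5% they are 6.90% and 5.95%, a difference of 0.95 points and a ratio of 1.16, against a true ratio of 2. The standard error of the difference, √(2p(1 − p)/170) with p the reported rate when q = 1% and r = 1, rises from 1.08 points (p0 = 0) to 1.51, 2.12 and 2.57 points (p0 = 1%, 3%, 5%).

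**Step 5: the open-label table.** A patient who crosses a limit at week 8 and stays there is a new case relative to the SAP 4.2 baseline, and so would count as new after 675 mg. Relative to the last value before the open-label dose, the same patient is carried over. Using only the first reference hides the carry-over. Using only the second would take out of the new cases an abnormality that began on monthly fremanezumab. Both are needed.

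**The case against.** The strongest reply is that SAP 8.5 is open about what it does. It says that all postbaseline values enter and never calls them new or treatment-emergent. A reader might infer from the word *incidence* that the SAP presents these cases as arising on drug. The documents do not support that: SAP 5.4 and 5.5 use the same word for medical history and prior medication, so here it means little more than patient counts.

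A reader might also infer that section 8.5 breaks a new-cases-only rule applied elsewhere. It does not. Under SAP 8.7 a systolic pressure of 182 mm Hg at baseline and 203 later (a rise of 21) is flagged although it was already beyond 180, and Table 4 sets no change condition for respiratory rate.

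Other points also stand:
- Exclusion q removes abnormalities judged clinically significant, and exclusion g removes significant hematological, renal and hepatic disease. Many Table 3 limits are marked enough to be weighed at screening, so baseline cases may be few.
- Clinically significant results are recorded as adverse events (Protocol 7.4), and treatment-emergent adverse events are summarized (SAP 8.3).
- Open-label summaries are shown by double-blind group (SAP 8.1), and the double-blind placebo column gives some background. Appearing once in each period's table is not double counting.
- No between-arm test of these rates is planned, so the loss of precision has little consequence.

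What remains is that no planned summary shows how many flagged patients were beyond the limit beforehand.

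**Conclusion.** The point holds as a minor gap in descriptive safety reporting. For chemistry, hematology and INR, the planned count mixes persisting pre-dose abnormalities with new ones. Taken as rates of new abnormality, the figures are overstated by an amount that the documents do not allow to be estimated. The gap bears mainly on tests without a numeric entry limit, and on the open-label table, which lacks a concurrent control.

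The percentages in the working rest wholly on assumed baseline prevalence, persistence and new-onset rates. They show how the count behaves and do not predict this trial; with no baseline cases nothing changes. A reader might infer a bias in favor of or against fremanezumab. The text does not support that: the rule applies alike to both randomized arms, so the comparison is diluted without a preferred direction. No efficacy endpoint, test or estimand is affected.

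**What to change.** In SAP 8.5, keep the all-postbaseline count as planned. Add a split by whether the Table 3 criterion was met at baseline, as defined in SAP 4.2. Report new cases with the patients who did not meet the criterion at baseline as the denominator, and show those beyond the limit both before and after dosing in their own row.

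For the open-label table, show status at that same baseline. As an additional row, not a replacement, also show status at the last value before the open-label dose, so that abnormalities arising during the double-blind period stay visible.

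Dropping baseline cases from the table altogether, or resetting the open-label baseline, would be a worse remedy. The first could hide worsening in patients already beyond a limit, and the second could hide abnormalities that began on monthly fremanezumab.

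The change uses data already scheduled for collection. The cost is a few more rows in one table and the programming of one baseline flag per criterion.
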